6.2 Assessment of Subject Compliance with Study Intervention/Investigational Product

Subject compliance will be measured by questionnaires as described in section 7.4.

6.3 Concomitant Medications/Treatments

6.3.1 Randomization

Any of the following medications, if applicable, that were administered within 14 days prior or ongoing at the time of randomization will be captured and reported to Advantage EDCSM:

- Steroids, topical only for GI GVHD and systemic (within 6 weeks prior to randomization)
- PUVA
- Immunosuppressant for acute or chronic GVHD (within 14 days prior to randomization, collect only start and stop dates)
- Preemptive or prophylactic antivirals (i.e. dosing of foscarnet, ganciclovir, valganciclovir, cidofovir, brincidofovir, letermovir, acyclovir/valacyclovir [high

and low dose], or any other investigational anti-CMV agent) (within 14 days prior to randomization).

• T-cell depleting agents including, but not limited to, anti-thymocyte globulin (ATG), alemtuzumab, etc. (any time after conditioning)

6.3.2 Quarterly Follow-Up

Following medications, if applicable, will be captured and reported to Advantage EDCSM during medical chart review at quarterly follow-up:

- Antiviral used for CMV treatment
- Steroids, topical only for GI GVHD and systemic

7 STUDY SCHEDULE

7.1 Screening

Every inclusion and exclusion criteria will be assessed by reviewing medical records or databases by the study coordinators. These will then be confirmed by site principal investigators to proceed for an informed consent meeting.

7.2 Enrollment/Baseline and Initial Study Visit

Enrollment will occur when discharge from the transplant service is imminent, generally near day 100 post-transplant (enrollment window day 60-180 post-transplant). The schedule of procedures is summarized in Appendix C.

At the enrollment visit, the following procedures will be performed for all study participants (e.g. DBS, Standard of Care, and Observational cohorts):

- Confirm eligibility (if screening and enrollment is not done on the same day)
- Confirm or obtain consent prior to proceeding with any study activities. (Refer to Section 4.2 for Observational cohort enrollment)
- Confirm recommended monitoring schedule.
- Randomization (not applicable for observational cohort)
- Counseling on the importance of adherence to the recommended CMV monitoring schedule (not applicable for Observational cohort)
- Collection of baseline data from subject charts (see manual of procedures)
 - o Age
 - Demographics
 - Medical history relating to:
 - Transplant
 - GVHD
 - CMV plasma reactivation or disease
 - Concomitant Medications

7.2.1 Enrollment and Initial Study Visit Procedures for Randomized DBS Arm

- Provision of DBS Self-Collection Kits (Refer to Section 6.1.1 and MOP) at each enrolling site (kits are assembled and distributed to each enrolling site by Fred Hutch)
- Training in finger-stick DBS collection for subjects and/or caregivers and sample shipping (refer to MOP)
- Training on the use of web and mobile technology tools with instructions provided in the manual of procedures from Emmes. Training includes:
 - Creation of login ID and password for website
 - Setting preferred communication method (SMS text or email)
 - Setting timeframe for receiving reminders and notifications
 - Using study website and mobile technology component
- Provision of Confirmatory Whole Blood Collection Kit (each kit to include one 6 mL EDTA tube with shipping box) at each enrolling site (kits are distributed to each enrolling site by Fred Hutch)
- Confirmation of integrity of the initial supply of DBS and plasma kits
- Instruction to provide plasma for central lab PCR testing at clinical blood draws

7.2.2 Enrollment Procedures for Randomized Standard of Care (SOC) Arm

Subjects who meet all inclusion and exclusion criteria, signed DBS CMV protocol consent form to participate in the trial, and randomized into standard of care arm will provide the same baseline characteristics via review of medical records. All following study activities of SOC arm, other than DBS collection, will be the same as DBS arm.

7.2.3 Enrollment Procedures for Observational Cohort

Subjects who meet all inclusion and exclusion criteria, declined DBS CMV protocol, but have signed medical records review consent at each participating transplant center will be enrolled in the control arm for retrospective chart review for CMV testing frequency at the time of discharge from transplant clinic, CMV disease, relapse, and mortality up to 1 year after HCT. Refer to Section 4.2.

7.3 Weekly DBS Testing

Subjects randomized to the DBS arm are instructed to collect DBS on the same day and at approximately the same time each week (Sunday through Wednesday to avoid delays due to weekend shipping) following the provided instructions (refer to MOP). Subjects will start weekly

DMID/NIAID/NIH CONFIDENTIAL DBS collections the week after discharge and continue until approximately 1 year after HCT even following a positive result or initiation of preemptive therapy. If a DBS participant is hospitalized, the participant should not collect weekly DBS samples during hospitalization. The admitting hospital should monitor the DBS participant for CMV with at least weekly plasma CMV DNA PCR testing during hospitalization. Once discharged, the study team will remind the participants to resume DBS collections according to their weekly schedules. The study team may provide a refresher DBS training if needed. If a subject's DBS result is positive, and/or prior to any initiation of standard-of-care preemptive therapy, a 6ml whole blood (EDTA anticoagulant tube) will be collected for plasma CMV PCR analysis by the subject's physician or referred collection site and an additional DBS sample at their scheduled laboratory visit with exemption to emergent hospital visit or hospitalization. Subjects will be provided with a pre-paid mailer with instructions to deliver to the collection center to assist with plasma CMV sample shipment to University of Washington Clinical Virology Laboratory on the day of collection. The subject will need to collect a DBS test at the time of the plasma collection. Subjects will be provided with a DBS kit to take with them to the physician's office. USPS should be contacted from the physician's office for pickup of the completed DBS kit.

All test results will be transmitted via a secure server to the study sites from the laboratory. The research staff will then contact the subjects' treating physicians via phone/fax. The subjects will receive a notification via the study web portal when their positive CMV test results are available with a link to a secure website that can be used to access them.

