3.3.8. Scheduled DBS Tests

Participants in the DBS arm were instructed to collect DBS on the same day and at approximately the same time each week (Sunday through Wednesday to avoid delays due to weekend shipping). If a DBS sample PCR result is missing, it is considered as noncompliant to the scheduled DBS test, i.e. missed recommended DBS tests.

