3.3.10. Confirmatory DBS Tests

Participants that were required to undergo confirmatory WB testing were also required to produce an additional confirmatory DBS sample to provide additional virologic data to assess the performance of the DBS assay. Confirmatory DBS tests are DBS tests entered on the CMV Laboratory Data Upload eCRF with the same collection date as the WB samples recorded on the CMV Laboratory Data Upload eCRF. Note that Confirmatory DBS Tests will not be used to assess any outcome measures related to adherence to the weekly DBS collection schedule but will be used to assess Unanticipated Adverse Device Effects (Section 3.3.14).

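### A weekly DBS collected on the day of a study blood draw is relabelled confirmatory by SAP 3.3.10 and lost from the exploratory missed-test counts

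*Protocol*

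**What the plan says.** Protocol 7.3 tells DBS-arm participants to "collect DBS on the same day and at approximately the same time each week" and to continue after a positive result. A study blood draw follows a positive DBS "and/or prior to any initiation of standard-of-care preemptive therapy", and at it the participant gives "an additional DBS sample at their scheduled laboratory visit". The same section repeats the requirement: "The subject will need to collect a DBS test at the time of the plasma collection". Draws are therefore not tied only to a positive DBS. The Protocol Summary also mentions periodic whole blood samples with an accompanying DBS, and Protocol 7.2.1 lists "Instruction to provide plasma for central lab PCR testing at clinical blood draws".

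SAP 3.3.10 describes the confirmatory DBS as an extra sample but defines it operationally by date alone: "Confirmatory DBS tests are DBS tests entered on the CMV Laboratory Data Upload eCRF with the same collection date as the WB samples". It adds: "Confirmatory DBS Tests will not be used to assess any outcome measures related to adherence to the weekly DBS collection schedule".

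SAP 3.3.8 says of the weekly schedule: "If a DBS sample PCR result is missing, it is considered as noncompliant to the scheduled DBS test". SAP 3.3.2 takes only hospitalization time out of the DBS-compliance period. Nothing in the SAP credits a weekly DBS collected on a draw date, keeps one of two same-day DBS as the scheduled one, or removes that week from the expected count.

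**The concern.** The date rule cannot separate the extra sample from the weekly one when both fall on the same date. If two DBS are taken, both match the WB date and both become confirmatory. If one is taken, it becomes confirmatory. Either way no DBS remains that may be used for that week, so the week falls into the missed-test counts.

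Exploratory objective 2 concerns non-compliance defined by a missing DBS PCR result. Here the result exists but may not be used. Tables 39 and 40 would then contain misses that did not happen. Because those tables set misses beside reminder, collection and delivery failures, some false misses could also be attributed to a mechanism that played no part. Two programmers could reasonably produce different counts from the same data.

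**Working it through.** **The plan's own figures.** SAP Appendix 4 gives expected weekly tests as N = floor((end date − discharge date + 1)/7).

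- Discharge at day 100, end at day 365: floor((365 − 100 + 1)/7) = floor(266/7) = 38, as in Protocol 11.1.1. The example there, 36/38 = 94.7%, also reproduces.
- SAP Example 1: floor(305/7) = 43, as stated.

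The SAP gives this formula for clinician-recommended tests. It is used here only to size a weekly DBS schedule.

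**The date rule applied to a perfect schedule.** Take N = 38, with a DBS on days 7, 14, …, 266 after discharge. A DBS on any WB date is confirmatory (3.3.10). A week with no remaining DBS is missed (3.3.8). A DBS is matched to a week if it lies within 3 days of the weekly date. That window is an assumption, because the SAP states none.

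| Case | DBS relabelled | Weeks missed | Completion |
|---|---|---|---|
| Week 10 DBS (day 70) positive, draw and extra DBS on day 73 | the extra one only | 0 | 38/38 = 100% |
| Draw on day 77 (week 11 DBS day), two DBS taken | both | 1 | 37/38 = 97.4% |
| Draw on day 77, one DBS taken | that one | 1 | 37/38 = 97.4% |

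**Cost per coincidence.** This is 1/N: 1/26 = 3.8 points, 1/38 = 2.6 points, 1/43 = 2.3 points. The values 26 and 43 are the ends of the anticipated participation range, in weeks, in Protocol section 4.

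**When the dates can coincide.** SAP 3.3.9 puts the confirmatory WB within 3 days of the positive DBS. The card must be mailed and tested before its result can trigger a draw, so such a draw falls after the positive DBS day and no later than day 3. The next weekly DBS is on day 7, so the two dates cannot meet. Three routes remain:

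1. A draw not timed by a positive DBS, such as one before preemptive therapy or a periodic draw.
2. A draw later than 3 days. Protocol 4.1 asks only for the earliest possible collection and sets no limit.
3. A weekly DBS moved from its usual day.

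The documents give no frequency for any of these.

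**The case against.** The strongest reply is that this will be rare and that nothing important depends on it. For draws that keep the 3-day interval after an on-schedule positive DBS, the rate is zero. Tables 39 and 40 are descriptive, and no hypothesis test uses them. It can also be said that the missed week is an inference: 3.3.8 speaks of a missing result, whereas here a result exists, and the SAP has no rule for matching a DBS to a week.

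Rarity and limited reach stand. The reply about inference does not remove the problem. Crediting the week would mean using a confirmatory DBS to assess weekly adherence, which 3.3.10 rules out, and no denominator exception covers the week.

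The same reply rules out stronger readings that a reader might infer:

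- **That participants drop below 90%.** Four coincidences give 34/38 = 89.5%, but the SAP applies no 90% line to DBS collection. Under SAP 3.3.5 and 4.5.1 the >90% status counts records on the Chart Review eCRF, and central-laboratory DBS results do not enter it.
- **That about one draw in five coincides.** This assumes draws spread evenly over weekdays regardless of the DBS date. It ignores the 3-day interval, and the documents do not support it.
- **That nearly every draw coincides because participants use the draw-day card as the weekly one.** Both documents call that card additional, and after an on-schedule positive DBS that week's scheduled sample already exists.
- **That the false misses concentrate in viraemic participants.** Draws prompted by a positive DBS are the ones that cannot coincide when the 3-day interval is kept.

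**Conclusion.** The defect is real and small. It lies in SAP 3.3.10 read with 3.3.8. Protocol 7.3 only establishes that a DBS is taken at the draw. A stated rule discards a valid weekly sample whenever a draw falls on the weekly DBS day, and each occurrence adds one false miss (2.6 points in the 38-test example).

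How often this happens cannot be estimated from the documents. The effect is confined to the exploratory DBS-compliance outputs, Tables 39 and 40. The primary endpoint is unaffected, provided it is computed as SAP 3.3.5 defines it. The conclusion also assumes that 3.3.10 is programmed literally and that a week left with no usable DBS is scored as missed.

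**What to change.** Add to SAP 3.3.8 and 3.3.10: when the WB collection date is the participant's scheduled weekly DBS day, one DBS collected that day counts as the scheduled weekly test. If two were taken, one is scheduled and the other confirmatory. If only one was taken, it serves both purposes. Apply this in Tables 39 and 40.

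The rule works on collection dates that 3.3.10 already uses. The weekly day could be taken from the DBS Testing Reminder eCRF (SAP 3.3.11), if the SAP says that this is its source. Classification by kit number is not a safe substitute. Listing 11 shows a kit number and a sample type of DBS or WB, but nothing indicates that the numbers distinguish confirmatory from weekly DBS.

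The cost is a sentence or two and a small programming change. There is one downside: a DBS collected at a clinic visit could be credited as a home collection, which could hide a genuinely missed home sample. Reporting the number of weeks credited this way, as a footnote to both tables, lets the reader judge that.

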7.4 Questionnaires

7.4.1 Subject Questionnaire

Subjects who are enrolled and randomized into DBS arm will be asked to complete a questionnaire at three different time points throughout study participation: after the third training session, one month after discharge from transplant clinic, and at the end of study. The questionnaire will solicit user feedback on the utility and clarity of the DBS collection training, reminders, and shipping instructions. The questionnaire will be provided via web/mobile technology by Emmes.

7.4.2 Provider Questionnaire

Primary care providers of subjects who are enrolled and randomized into DBS arm will be asked to complete a questionnaire at the end of subject's study participation. The questionnaire will solicit the provider's feedback on the utility and quality of the DBS testing. The questionnaire will be provided via fax by study coordinators at the time of last quarterly follow up records request.

7.5 Follow-up (Quarterly, ± 2 weeks)

Quarterly follow-up contacts will be done on all randomized subjects while enrolled in the study regardless of the randomization status. Study sites will follow up with subjects' primary care physicians to obtain the following records at each quarterly time point based on transplant date:

- Current immunosuppression
- Systemic steroid use
- Recommended CMV test interval (i.e., testing frequency)
- Office-based CMV test dates and results (i.e. PCR, IHC, histopathology, etc.)
- Interim hospitalizations
- CMV disease status
- Interim use of preemptive therapy for late CMV disease
- AEs
- Date of morphological relapse
- Survival status
- Problems with DBS or plasma kit integrity

If the scheduled quarterly visit is within 10 days of subject randomization, the corresponding quarterly visit will be waived.

7.6 Final Study Visit

At approximately 12 months after HCT (+4 months), study staff will conduct a closeout data collection of both randomized and observational cohorts by obtaining subject's medical records. The following information should be recorded on the appropriate electronic case report form:

- Current immunosuppression
- Systemic steroid use
- Recommended CMV test interval (i.e., testing frequency)
- Office-based CMV test dates and results (i.e. PCR, IHC, histopathology, etc.)
- Interim hospitalizations
- CMV disease status
- Interim use of preemptive therapy for late CMV disease

DMID/NIAID/NIH CONFIDENTIAL

- AEs
- Date of morphological relapse
- Survival status
- Problems with DBS or plasma kit integrity

7.7 Hospitalizations

If a study subject is hospitalized, both the clinical trial coordinating center (Fred Hutch) and local site should be informed by the study coordinator or admitting physician, respectively. Subjects will be provided a letter that includes information about the study (i.e., study synopsis), which should be given to the admitting physician (refer to MOP). Information includes a short description of the study, instructions for hospital monitoring for CMV during the hospitalization, and contact information (phone, fax, and email).

If a DBS study participant is hospitalized, the participant should not collect weekly DBS, and local CMV monitoring with plasma CMV DNA PCR testing should be performed during the hospitalization.

8 STUDY PROCEDURES/EVALUATIONS

8.1 Laboratory Evaluations

8.1.1 Clinical Laboratory Evaluations

8.1.1.1 Plasma CMV PCR Testing

Subject plasma samples will be tested for CMV viral load at the University of Washington Molecular Virology Laboratory using a validated qPCR assay that targets two CMV genes (i.e., UL55 and UL123) simultaneously using TaqMan probes, standard primers, and a single FAM fluorophore ^{40,41}.

8.1.2 Special Assays or Procedures

8.1.2.1 CMV DBS PCR Testing

Subject DBS samples will be tested for CMV viral load at the University of Washington Molecular Virology Laboratory using a slightly revised and optimized version of the assay described in Limaye, et al ³⁴. In this assay, a single-use paper punch is used to punch a DBS from the Whatman 903 Protein Saver Card. DNA is extracted from the DBS (after washing) by adding 100 μ l of autoclave-sterilized 5% Chelax (Bio-Rad) and incubating at 95°C for 30 minutes (per manufacturer instructions). 20 μ l of eluted DNA are used for real-time TaqMan CMV PCR (as described in ⁴⁰) of a 50 μ l PCR mixture containing 25 μ l of 2× QuantiText multiplex PCR master mix (Qiagen) a 415 nM concentration of each primer (gB and IE-Ex4), and 100 nM concentration of the probes (gB and IE-Ex4).

8.1.3 Specimen Preparation, Handling, and Shipping

8.1.3.1 Specimen Collection and Transport to Processing Laboratory

DBS specimen:

Subjects are instructed to schedule same day or next morning (for evening DBS collection) mail carrier pick-up by website or phone or to deliver the envelope to the post office for overnight shipping with provided prepaid mailing envelopes. Subjects are to schedule pick up from Monday through Wednesday to avoid delays due to weekend shipping.

Plasma CMV PCR specimen:

Subjects are instructed to have 6ml EDTA drawn at their primary oncologist's office, primary transplant center, or blood draw facility, whichever is clinically scheduled, once their DBS is resulted positive or prior to initiation of preemptive therapy. The plasma sample will be sent from the collection center using the provided instructions and supplied prepaid mailing envelopes (which meet the biohazard shipping requirement) via overnight FedEx delivery. To ensure specimen's viability, processing laboratory must receive the sample within 48 hours of collection.

Detailed instruction regarding specimen collection and shipping will be provided to the subject at the time of training, prior to discharge from primary transplant clinic. All subjects will be provided with supplies with subject ID.

All specimens (both DBS and plasma) will be shipped to University of Washington Clinical Virology Laboratory ([name]) for analysis.

Specimen collection kits will be supplied by the coordinating center, Fred Hutch, to each site where they will be distributed to participating subjects.

8.1.3.2 Specimen Processing and Storage

Specimen processing and storage will occur at University of Washington Clinical Virology Laboratory. Samples will be labeled with date of collection, study protocol number, and subject ID. Leftover of plasma samples from EDTA tubes will be stored at -80 °C.

9 ASSESSMENT OF SAFETY

9.1 Adverse Events

AEs will be elicited from subjects in the DBS arm at quarterly follow-up contacts and at the final closeout contact.

For this trial, a reportable AE is defined as any clinically important untoward medical experience directly related to DBS collection, that is, the finger-stick procedure. The study source documents will include the assessment and evaluations of all AEs as defined above.

Only those events that are considered "Severe" and "Related" to the DBS collection and finger stick procedure will be reported. See below for definition of "Severe" and "Related":

- Severe: Events interrupt a subject's usual daily activity and require systemic drug therapy or other medically administered treatment.
- Related: There is a reasonable possibility that the study product caused the adverse event. Reasonable possibility means that there is evidence to suggest a causal relationship between the study product and the adverse event.

AEs as defined above are reported on appropriate CRFs in the AdvantageEDCSM.

If an AE is considered "Unexpected", the appropriate CRF must be submitted within 10 calendar days.

 Unexpected: Event is not listed in study materials or is not listed at the specificity or severity that has been observed; or is not consistent with the risk information described in the general investigational plan. For example, under this definition, an infection requiring antibiotic treatment and causing a missed day of work may be considered Expected. An infection causing an extended absence from work or leading to necrosis may be considered Unexpected.

DMID Medical Monitor will review adverse events and determine if additional reporting is applicable.

9.3 Unanticipated Problems

Investigators must report Unanticipated Problems, regardless of severity, associated with self-administered finger-stick DBS collection or assay. This includes false positive or false negative assay results. An Unanticipated Problem is defined as:

Any incident, experience, or outcome that meets all of the following criteria:

• Unexpected, in terms of nature, severity, or frequency, given the research procedures that are described in the protocol-related documents, such as the IRB-approved research protocol and informed consent document; and the characteristics of the subject population being studied

• Related or possibly related to participation in the research, in this guidance document, possibly related means there is a reasonable possibility that the incident, experience, or outcome may have been caused by the procedures involved in the research

The investigator shall submit to DMID and to its local IRB a report of any Unanticipated Problem occurring during an investigation as soon as possible, but in no later than 10 working days or per local guidelines, respectively, after the investigator first learns of the effect.

DMID as the sponsor shall immediately conduct an evaluation of any Unanticipated Problem. If an Unanticipated Problem presents an unreasonable risk to subjects, DMID shall terminate all investigations or parts of investigations presenting that risk as soon as possible. Termination shall occur no later than 5 working days after the sponsor makes this determination and no later than 15 working days after the sponsor first received notice of the effect. Resumption of any termination will not occur without FDA and IRB approval. (21 CFR 812.46)

If DMID conducts an evaluation of an Unanticipated Problem under 21 CFR 812.46 (b) then DMID will report the results of such evaluation to FDA and to all participating investigators no later than 15 working days after DMID first receives notice of the effect. Clinical site investigators and Coordinating Center shall report to IRBs per local guidelines after receipt of evaluation from DMID. Thereafter DMID will submit such additional reports concerning the effect as FDA requests.

